## **8.0 ASSESSMENT OF EFFICACY**

As per the OGD guidance, primary efficacy endpoint is the mean difference in IOP of both eyes between the 2 treatment groups at 4 time points, i.e., at approximately 8:00 a.m. (hour 0; before the morning drop) and 10:00 a.m. (hour 2) at the Day 14 (Week 2) and Day 42 (Week 6) visits

This will be done by measuring IOP at 08:00 AM  $\pm$  30 min and at 10:00 AM  $\pm$  30 min using Goldmann applanation tonometer at the baseline visit (Visit 2) and at the Day 14 (Week 2) and Day 42 (Week 6) visits.

The secondary efficacy endpoint is change from baseline in IOP of both eyes between the 2 treatment groups at 4 time points, i.e., at approximately 8:00 AM (hour 0; before the morning drop) and 10:00 AM (hour 2) at the Day 14 (Week 2) and Day 42 (Week 6) visits.

## **9.0 ASSESSMENT OF SAFETY**

### **9.1 Description of Safety Parameters**

The following ocular safety assessments will be done during the study as per the Schedule of Assessments

The order of assessment will be the following:

1. BSCVA
2. Slit lamp biomicroscopy
3. Goldmann tonometry
4. Dilated ophthalmoscopy, including recording cup/disc ratio

### **9.2 Definitions of Adverse Events**

#### **9.2.1 Adverse Event**

An AE is any untoward medical occurrence in a clinical investigation subject administered a drug and does not necessarily have a causal relationship with this treatment. An AE can therefore be any unfavorable and unintended sign (including an abnormal laboratory finding), symptom, or disease temporally associated with the use of a study medication (investigational), whether or not related to the study medication (investigational).

Untoward medical experience occurring during medication-free pre-treatment periods does not meet the above-mentioned definition of an AE. Nevertheless, they have to be documented in the same way as AE. Each subject will be queried generally for the occurrence of adverse experiences prior to study medication administration and throughout the subject's participation in the study. During and following a subject's participation in this study, the Investigator has to ensure that adequate medical care is provided to a subject for any AE, including clinically significant laboratory values. The subject will be treated and/or followed up until the symptom(s) return to normal, as judged by the Investigator.

### 9.2.2 Serious Adverse Event

A SAE is any untoward medical occurrence that, at any dose

- Results in death
- Is life-threatening
- Requires in-subject hospitalization or prolongation of existing hospitalization\*
- Results in persistent or significant disability/incapacity
- Is a congenital anomaly/birth defect
- Important medical event: Important medical events that may not result in death, be life-threatening, or require hospitalization may be considered as SAEs when, based upon appropriate medical judgment, they may jeopardize the subject or may require medical or surgical intervention to prevent one of the outcomes listed above. Examples of such events include allergic bronchospasm requiring intensive treatment in an emergency room or at home, blood dyscrasias (e.g., neutropenia or anemia requiring blood transfusion, etc.), convulsions that do not result in hospitalization, or the development of drug dependency or drug abuse.

NOTE: The term "life-threatening" in the definition of "serious" refers to an event in which the subject was at risk of death at the time of the event; it does not refer to an event, which, hypothetically, might have caused death if it were more severe.

\*A planned hospitalization for pre-existing condition, or a procedure required by the Clinical Investigation Plan, without a serious deterioration in health or if the hospitalization is clearly not associated with an AE (e.g., hospitalization due to social / logistic reason) are not to be considered as SAEs.

### 9.3 Pregnancy

Women of childbearing potential must agree to the use of a reliable method of contraception (e.g., total abstinence, intrauterine device, a double-barrier method [such as condom plus diaphragm with spermicide], oral, transdermal, injected or implanted non- or hormonal contraceptive), throughout the study. A sterile sexual partner is not considered an adequate form of birth control. Subjects on hormonal contraceptives must have been on the same hormonal contraceptive for at least 1 month before the Screening and continue throughout the duration of the study.

A female is considered of childbearing potential if she has had her first menses and she is either:

- a. not postmenopausal for at least 12 consecutive months prior to enrollment; or
- b. not surgically sterilized by bilateral tubal ligation, or bilateral oophorectomy, or hysterectomy
- c. Male subjects with partners of childbearing potential who are not using birth control as described above must use a barrier method of contraception (e.g., condom) if not surgically sterile (i.e., vasectomy).

Male subjects enrolled in the study will be instructed to avoid passage of semen to their partner by using an acceptable contraceptive method to avoid fathering a child. If a female subject becomes pregnant during the study, the pregnancy will be recorded as a significant medical event and reported per SAE reporting procedures and the subject will be withdrawn from the study immediately. If a female partner of a male subject becomes pregnant during the study, the medical event will be recorded appropriately with the 'Pregnancy Reporting Form' and submitted to the Sponsor's safety physician/CRO. All pregnancies shall be followed every 3-months until outcome and up to one month post delivery to assess the functional status of the child. If any SAE occurs during pregnancy then it will be reported using SAE forms. Any congenital abnormalities or birth defects in the newborn will be followed 3-months post delivery.

#### 9.4 Eliciting, Documentation and Reporting of Adverse Events

Information on AEs will be derived by questioning the subjects in general terms (e.g., "How do you feel?" or "How have you been feeling since the last questioning?" respectively), by subjects' spontaneous reports, or by observation.

Adverse events will be documented on the source document. Trained monitors will check the entries on the source document. The AE will be transcribed to the AE eCRF-sections. The following information will be given for each AE: description of the AE, start date, stop date, severity, pattern, action taken, outcome, seriousness, dose of study drug, and relationship to the study medications. The dose of study medication assigned to an AE will be the dose the subject was assigned to take on the date the subject reported the AE first began.

The AE/SAE collection period for safety surveillance begins when the subject signs the ICF and continues until the end of treatment visit or until the last dose of study medication for subjects with early discontinuation. Adverse events with an onset before the subject receives first dose of the study medication will be categorized as non-treatment emergent AEs (non-TEAEs). Adverse events with an onset after at least 1 dose of study medication is received will be reported as TEAEs.

Safety reporting is inline with the local regulatory requirements in which the study will be conducted.

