#### 3.2.3.1 Pharmacokinetics:

Following topical ocular administration, brinzolamide is absorbed into the systemic circulation. Due to its affinity for CA-II, brinzolamide distributes extensively into the RBCs and exhibits a long half-life in whole blood (approximately 111 days). In humans, the metabolite N-desethyl brinzolamide is formed, which also binds to CA and accumulates in RBCs. This metabolite binds mainly to CA-I in the presence of brinzolamide. In plasma, both parent brinzolamide and

N-desethyl brinzolamide concentrations are low and generally below assay quantitation limits. An oral pharmacokinetic study was conducted in which healthy volunteers received 1 mg capsule of brinzolamide twice per day for up to 32 weeks. This regimen approximates the amount of drug delivered by topical ocular administration of Azopt® (brinzolamide ophthalmic suspension) 1% dosed to both eyes three times per day and simulates systemic drug and metabolite concentrations similar to those achieved with long-term topical dosing. Red blood cell CA activity was measured to assess the degree of systemic CA inhibition. Brinzolamide saturation of RBC CA-II was achieved within 4 weeks (RBC concentrations of approximately 20 mcM). N-desethyl brinzolamide accumulated in RBCs to steady-state within 20 to 28 weeks reaching concentrations ranging from 6 to 30 mcM. The inhibition of CA-II activity at steady-state was approximately 70 to 75%, which is below the degree of inhibition expected to have a pharmacological effect on renal function or respiration in healthy subjects.

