### **6.3.4 End of treatment/Visit 4 (Week 6 ± 4 days)**

- Concomitant medications
- AE assessment (reported, elicited, observed)
- Urine pregnancy test (if applicable)
- Review study medication compliance diary
- Collect the study medication and medication diary
- Heart rate and blood pressure
- BSCVA
- Slit lamp biomicroscopy
- Intraocular pressure at 08:00 AM ± 30 min and at 10:00 AM ± 30 min by Goldmann applanation
- In house study medication instillation (8:00 AM ± 30 min dose) after IOP reading
- Dilated ophthalmoscopy
- Study exit

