### **6.3.5 End of Study Visit 5: Telephonic Visit (Week 7 ± 4 days)**

A telephonic call will be done from the study site personnel to the subject after at least 1 week ± 2 days of end of treatment visit 4 (Week 6 ± 2 days). This is to ensure the overall well being of the subject.

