### **6.3.6 Early Discontinuation (ED) Visit**

An Early Discontinuation (ED) Visit will occur if a subject requests to withdraw from the study or is asked to withdraw by an Investigator (withdrawal rules). Document reason of subject's termination from study participation, record timing subject took dose of study drug prior day and on day of visit and perform all procedures that are applicable for Visit 4 /End of Treatment Visit (Week 6±2 days).

Subjects whose condition worsens (e.g., IOP  $\geq$  36 mm Hg in either eye) and require alternate or supplemental therapy for the treatment of their chronic open angle glaucoma or ocular hypertension during the study should be discontinued, excluded from the per protocol (PP) population analysis, and provided with effective treatment.

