#### **9.8.2 Post-study Events**

Any AE/SAE which occurs past the end of the treatment visit will be reported if it is considered related to study drug by the Investigator.

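### Protocol 9.4 ends AE/SAE collection at the last dose (early discontinuers) or Visit 4 (completers), which conflicts with the AE assessment at the ED visit and leaves out the scheduled Week 7 call

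*Protocol*

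**What the plan says.** - **Protocol 9.4** starts AE/SAE collection at consent and says that it "continues until the end of treatment visit or until the last dose of study medication for subjects with early discontinuation".
- **Protocol 6.3.6** requires a subject who leaves early to "perform all procedures that are applicable for Visit 4 /End of Treatment Visit". **Protocol 6.3.4**, which lists those procedures, includes "AE assessment (reported, elicited, observed").
- **Protocol 9.2.1** asks for every subject to be queried about adverse experiences before dosing and for the whole of their participation.
- **Protocol 6.3.5** schedules a telephone call about a week after Visit 4 and titles it the end-of-study visit. Its only stated purpose is: "This is to ensure the overall well being of the subject". The synopsis counts this week in the total study duration.
- **Protocol 9.8.2** says that an AE or SAE occurring after the end of treatment visit "will be reported if it is considered related to study drug by the Investigator".
- **SAP 8.3 and 9.6.3.1** say when an event becomes treatment-emergent. They do not say when the treatment-emergent period ends.

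**The concern.** The protocol gives sites more than one answer on when to stop recording adverse events. An event that begins after an early discontinuer's last dose and is mentioned at the ED visit is elicited under 6.3.6 but lies outside the window in 9.4. For completers, 9.4 closes the window before the last scheduled contact with the subject, and that contact has no stated role in AE collection.

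Safety is the only secondary objective, and incidence and severity of AEs is its lead measure. If sites resolve the conflict differently, the safety record depends in part on which section a site follows. Because the SAP sets no end to the treatment-emergent period, it does not settle whether an event recorded after the 9.4 cut-off is counted. Events judged unrelated, SAEs included, have no clear collection rule after Visit 4.

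**Working it through.** The plan gives no figure to reproduce here, so the check sets the rules side by side by time of onset.

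| Onset of event | Under 9.4 | Under other sections | Result |
|---|---|---|---|
| Early discontinuer, up to last dose | Inside window | AE withdrawals followed for outcome (6.5) | Collected |
| Early discontinuer, after last dose and up to ED visit | Outside window | Elicited at the ED visit (6.3.6 with 6.3.4); queried (9.2.1); 9.8.2 names only the end of treatment visit | Sections conflict |
| Completer, up to Visit 4 | Inside window | AE assessment at Visit 4 (6.3.4); ongoing events followed (9.8.1) | Collected |
| Completer, Visit 4 to call, judged related | Outside window | Reportable (9.8.2) | Reported if it comes to notice |
| Completer, Visit 4 to call, judged unrelated | Outside window | Not reportable under 9.8.2; 9.2.1 would still have it asked about | Not collected if 9.4 and 9.8.2 are followed |

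**Are discontinuers cut off earlier than completers, relative to dosing?** Section 6.3.4 lists "In house study medication instillation (8:00 AM ± 30 min dose) after IOP reading" at Visit 4. The completers' window therefore closes on the day of their last scheduled dose. Neither group has a collection period after dosing under 9.4.

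**Length of the completers' gap (Visit 4 to call).**
- Nominal: Day 49 − Day 42 = 7 days.
- With the ± 2 days in the text of 6.3.5: 7 − 2 = 5 to 7 + 2 = 9 days.
- If the ± 4 days in the heading of 6.3.5 is applied to the interval: 7 − 4 = 3 to 7 + 4 = 11 days.

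The heading and the text of 6.3.5 disagree on this tolerance, which should be settled in the same edit.

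**Length of the discontinuers' gap (last dose to ED visit).** No section gives it, so it cannot be computed.

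**Number of early discontinuers.** The only planning figure is the 20% non-evaluable allowance: 666 − 532 = 134 subjects. That total includes subjects with major protocol violations, so it is a planning ceiling and not an estimate.

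**Number of events affected.** This would be subjects × event rate per day × days in the gap. The documents give no event rate after the last dose, and for discontinuers no gap length either. The product cannot be formed.

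**The case against.** The strongest reply is that little is lost in practice.

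- **AEs are elicited at the ED visit.** This is correct. What stands is a contradiction between sections. A reader might infer from 9.4 that collection simply stops before the ED visit, but 6.3.6 with 6.3.4 says otherwise.
- **Related events stay reportable, on a broad definition.** Section 9.5 calls an event related when a causal link cannot be excluded, and unrelated only when it is clearly due to something else. The loss for completers is therefore mainly of clearly extraneous events. This narrows the point but does not remove it, because comparing AE incidence between arms does not depend on investigator attribution.
- **SAEs are covered elsewhere.** Section 9.7 requires all SAEs to be reported under ICH GCP or local rules, whichever is stricter. However, 9.4 sets the collection period for SAEs as well as AEs, and 9.8.2 limits late SAEs to related ones. The sections still need to be reconciled.
- **The schedule may already cover the call.** Table 1-1 is redacted and may show AE assessment at Visit 5. That is possible, but the text of 6.3.5 does not say so and 9.4 would still close the window earlier.

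Four stronger readings are tempting, and the documents do not support them.

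- **Under-collection in those most likely to have events.** An AE that leads to stopping normally starts on or before the last dose, inside the window, and is followed for outcome. Completers' collection also ends on a dosing day.
- **Bias between arms.** The rule is the same in both arms and the investigator is masked. Nothing in the documents shows that discontinuation differs by arm.
- **Continuing exposure.** Section 3.2.3.1 says that the drug "exhibits a long half-life in whole blood (approximately 111 days"). The same section says that plasma concentrations are generally below the limits of quantitation. One further week is 7/111, about 6% of that half-life. The half-life therefore does not justify this particular extension.
- **A 14% loss of follow-up.** One week out of 6 + 1 weeks is 14% of time on treatment and follow-up. Counting the 6 weeks of screening that 9.4 also covers, it is 1/13, about 8%. Either is a share of time, not of events, and related events in that week remain reportable.

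**Conclusion.** The point holds as a conflict between sections that, if 9.4 is followed literally, gives a less complete safety record. It affects two groups of events: those starting between last dose and the ED visit in early discontinuers, and those judged unrelated, SAEs included, in the roughly 7 days (5 to 9 by the text of 6.3.5) between Visit 4 and the call.

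The size cannot be stated as a number of events. The conclusion rests on reading 9.4 and 9.8.2 as written and on the visible text of 6.3.5, since the schedule table is redacted. It is worth correcting because the fix uses contacts already planned.

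**What to change.** - **Protocol 9.4:** collect AEs and SAEs of any causality from consent through the ED visit for early discontinuers and through the scheduled Week 7 call for completers.
- **Protocol 6.3.5:** state AE assessment as part of the call, check that Table 1-1 agrees, and give one tolerance for the timing of the call.
- **Protocol 9.8.2:** restrict it to events after the new end of collection, and word it for both completers and early discontinuers.
- **SAP 8.3 and 9.6.3.1:** define an end to the treatment-emergent period that matches.

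If conduct is too far advanced for a protocol amendment (the SAP is dated 20 Sep 2023), the SAP can still define that end before database lock and say how events recorded at the ED visit or the call are handled.

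The cost is wording, one AE question at a call that is already made, and slightly higher AE counts. No additional call for early discontinuers is needed.

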#### 9.5 Causality of Adverse Events

The relationship of AEs to study medication will be assessed by the Investigator, and will be a clinical decision based on all available information. Following definitions shall be used for assessment of causality.

| Category  | Definition   |
|-----------|--|
| Unrelated | Those adverse events (AEs) which, after thorough assessment, are clearly due to extraneous causes (disease, environment, etc.) |
| Related   | The causal relation between the study medication and event cannot be excluded  |

The Investigator should consider the following, for causality assessment:

- Time relationship between study medication intake and event's onset

- Dechallenge
- Rechallenge
- Medical history
- Study treatment
- Mechanism of action of study medication
- Concomitant medications in use
- Lack of efficacy/worsening of existing condition
- Erroneous treatment with study medication or concomitant medication
- Protocol-related procedure.

### **9.6 Assessment of severity, outcome and expectedness of Adverse Events**

The severity of an AE will be characterized as:

- Mild: AE which is easily tolerated
- Moderate: AE sufficiently discomforting to interfere with daily activity.
- Severe: AE, which prevents normal daily activities.
- Life-threatening: The subject is at risk of death due to the AE as it occurred. This does not refer to an event that hypothetically might have caused death if it were more severe.
- Death: Death related to AE

Event outcome or time last follow-up is recorded is categorized as “fatal”, “resolved”, “resolved with sequelae”, “resolving”, “not resolved”, or “unknown”.

Action taken with respect to study drug is categorized as “none”, “study medication discontinued / withdrawn”, “study medication discontinued and restarted”, “required concomitant medication”, “required procedure”, or “other”.

Assessment of Expectedness will be determined by the version of the IB effective at the time of onset of the adverse event.

### **9.7 Documentation and Reporting of Immediately Reportable Adverse Events**

All SAEs must be reported according to ICH GCP or local regulations, applying the regulation with the stricter requirements. The report will contain as much available information concerning the SAE to enable the Sponsor’s safety physician/CRO to file a report, which satisfies regulatory reporting requirements. The SAE report will be notified by Investigator within 24 hours of his / her awareness to the Sponsor’s safety physician/CRO. These timelines apply to initial reports of SAEs and to all follow-up reports.

All AEs/SAEs will be recorded on the AE/SAE Report Form in the eCRF and source documents. As much information as possible should be supplied at the time of the initial report with at least the following information using SAE Report Form:

- Name, address, and telephone number of the reporting Investigator
- Investigational product(s) (study medication)

- Protocol number
- Subject identification number, initials, sex and date of birth
- Description of the AE, reason considered serious, measures taken and outcome (if resolved)
- Likelihood of drug causation of the AE assessed by the Investigator.
- Additional follow-up information should be completed on an SAE follow-up form with a copy sent to the Sponsor's safety physician/CRO.

In exceptional circumstances, an SAE (or follow-up information) may be reported by telephone. In these cases, a written report must be sent immediately thereafter by email to the Sponsor's safety physician/CRO.

Relevant pages from the source document and eCRF may be provided in parallel (e.g., medical history, and concomitant drugs). Additional documents may be provided by the Investigator, if available (e.g., laboratory results, hospital report, and autopsy report). In all cases, the information provided on the SAE Report Form must be consistent with the data about the event recorded in the eCRF.

The Investigator must respond to any request for follow-up information (e.g., additional information, outcome, final evaluation, and other records where needed) or to any question the Sponsor's safety physician/CRO may have on the SAE. This is necessary to ensure prompt assessment of the event by the Sponsor's safety physician to allow the Sponsor to meet strict regulatory timelines associated with expedited safety reporting obligations.

Requests for follow-up will usually be made via the Sponsor's safety physician/CRO.

#### **9.7.1 Serious Adverse Events/Suspected Unexpected Serious Adverse Reactions (SUSARs) Reporting to Regulatory Authorities/EC/IRBs/Participating Investigators**

The applicable Regulatory Authorities shall be notified by Sponsor Safety Physician/CRO of any SAE/SUSAR, as per local Regulatory Authorities guidelines and timeframe specified as per local regulation.

All participating Investigators, EC/IRB and other stakeholders shall be notified of any SAE/SUSAR by CRO as per local regulatory requirement.

For any SAE, the Investigator must notify the contact person listed below immediately:

|  |  |
|--|--|
|  |  |
|  |  |

The Investigator is obligated to pursue and provide information to Sponsor and the responsible CRO on all SAEs in accordance with the timeframes for reporting specified above. In addition, an Investigator may be requested by Sponsor and the responsible CRO to obtain specific additional

follow-up information in an expedited fashion. This information may be more detailed than that captured on eCRF. In general, this will include a description of the SAE, which should be provided in sufficient detail so as to allow for a complete medical assessment of the case and independent determination of possible causality. Information on other possible causes of the event, such as concomitant medications and illnesses must be provided. In the case of a subject death, a summary of available autopsy findings must be submitted as soon as possible to Sponsor or its designated representative.

The initial reports should be followed promptly by detailed written reports. The initial and follow-up reports should identify patients by unique code numbers assigned to the trial patients rather than by the patients' names, personal identification numbers, and/or addresses.

Exposure In Utero During Clinical Studies

If a patient becomes pregnant during the treatment period or within 7 days after the last dose of study treatment, she must not receive additional study drug or treatment and must be promptly discontinued from the study. The patient must be followed up until the outcome of the pregnancy is known (i.e., delivery, elective termination, or spontaneous abortion). If the pregnancy results in the birth of a child, additional follow-up information may be requested.

The Investigator must notify the responsible CRO (at the below mentioned e-mail address) within 24 hours of first learning of the occurrence of pregnancy using the Pregnancy Notification Form providing as much information as possible. The Investigator must notify the responsible CRO about reported complications within 24 hours using the same procedure. Outcome of pregnancy, once known by the Investigator, must also be reported to the responsible CRO within 24 hours using the Pregnancy Outcome Form. Pregnancy communications will be directed to:

|  |
|--|
| Pregnancy Reporting Contact Details Email |
| [REDACTED]                                       |

Contract Research Organization who will relay pregnancy notifications to Sponsor. Please note that pregnancy in and of itself is not an AE or SAE. Pregnancy should not be entered into the CRF as an AE unless the Investigator suspects an interaction between the study treatment and contraceptive method. Pregnancy will be documented as the reason for study discontinuation.

CRO will direct the pregnancy communication to Sponsor (Pharmacovigilance Responsible Person) as soon as it is received.

|            |            |
|------------|------------|
| [REDACTED] | [REDACTED] |
|------------|------------|

|  |            |
|--|------------|
| [REDACTED]   | [REDACTED] |
| The following generic email should be present in all communications:
[REDACTED] |            |

Progress reports: Where required by applicable regulatory requirements, the investigator should submit written summaries of the trial's status to the institution. The investigator/institution should submit written summaries of the status of the trial to the IRB/EC annually, or more frequently, as requested. The Investigator should promptly provide written reports to the Sponsor, the IRB or EC, and, where required by the applicable regulatory requirements, the institution on any changes significantly affecting the conduct of the trial, and/or increasing the risk to the subjects.

